1.19 Serious Adverse events

1.19.1 General definition

An adverse event (AE) is any expected or unexpected harmful and unintended occurrence or exacerbation in a clinical trial subject, whether or not related to the trial or the investigational product. It can be a new intercurrent disease, exacerbation of a concomitant disease, an accident, or any other deterioration in the patient's health, including abnormal laboratory findings. All AEs will be reported from the time that consent is obtained.

Any medical condition that existed before the start of the study treatment and that remains unchanged or improves must not be recorded as an AE. If a medical condition worsens, it must be recorded as an AE. The diagnosis or syndrome rather than the individual signs or symptoms must be recorded on the AE pages of the case report form.

An event is considered a serious adverse event (SAE) if it:

- Results in death; Death due to disease progression is excluded
- Is life-threatening,
- Requires inpatient hospitalization or prolongation of existing hospitalization,
- Cause any persistent or significant disability/ incapacity,
- Causes a congenital anomaly, birth defect or abortion,
- Is a new cancer (that is not the condition of the study)
- Is associated with an overdose
- Is another medically significant event

The terms *disability* and *incapacity* refer to any clinically significant physical or mental handicap, whether temporary or permanent, that affects the patient's physical activity and/or quality of life.

A *medically significant* event is any clinical event or laboratory finding considered by the investigator to be serious that does not meet the seriousness criteria defined above. It may pose a risk to the patient and require medical intervention to prevent one of the serious outcomes mentioned previously (e.g. *an overdose, second cancer, pregnancy, and new information can be considered medically significant*).

The following are not considered as serious adverse events:

- Death due to disease progression
- Hospitalization for < 24 hours
- Hospitalization scheduled before the start of the trial and/or stipulated in the protocol (e.g. for biopsy or chemotherapy)

The AE pages of the case report form and an SAE form should be completed for each AE considered serious.

For each AE, the investigator shall provide information about the intensity, start and end dates, causality, the action taken, and the outcome

1.19.2 Definition of an expected serious adverse event (SAE-E)

An expected SAE is an event already mentioned in the most recent version of the Investigator Brochure, or in the Summary of Product Characteristics (SmPC) for medicinal products that have already been granted marketing authorization (MA). This definition also applies to the trial drug when it is administered for the same population but for an unlicensed indication.

1.19.3 Definition of an unexpected serious adverse event (SAE-U)

Any adverse drug experience, the specificity or severity of which is not consistent with the current investigator brochure; or, if an investigator brochure is not required or available, the specificity or severity of which is not consistent with the risk information described in the general investigational plan. “Unexpected” as used in this definition, refers to an adverse drug experience that has not been previously observed (e.g., included in the investigator brochure) rather than from the perspective of such experience not being anticipated from the pharmacological properties of the pharmaceutical product. [21CFR312.32(a)]

1.19.4 Intensity

The term *intensity* (severity) should not be confused with the term *seriousness* that serves as a guide for defining reporting obligations.

The intensity of events shall be evaluated according to the excerpt from the CTC-AE classification, version 4.0 (Appendix 7). The intensity of adverse events not listed in this classification will be rated using the following terms:

Mild (grade 1): does not affect the patient’s usual daily activities

Moderate (grade 2): interferes with the patient’s usual daily activities

Severe (grade 3): prevents the patient’s usual daily activities

Very severe (grade 4): requires intensive care / is life-threatening

Death (grade 5)

1.19.5 Causal relationship between an adverse event (SAE/AE) and the study treatment

Assessment of attribution is made by consideration of all clinically relevant data prior to, during, and after occurrence of the event, including diagnostic tests to assess the cause of the event. Clinically relevant data include, but are not limited to; underlying disease, past and present medical history (all concurrent non-malignant disease), concurrent medications, and timing between event and drug administration. The mechanism of action and prior toxicology of the study drug should be considered.

An adverse event is *associated with the use of the drug* when there is a reasonable possibility that the experience may have been caused by the drug. [21CFR312.32(a)]

Attribution Standards per NCI – CTEP:

Unrelated	The Adverse Event is clearly not related to the investigational agent(s)
Unlikely	The Adverse Event is doubtfully related to the investigational agent(s)
Possible	The Adverse Event may be related to the investigational agent(s)
Probable	The Adverse Event is likely related to the investigational agent(s)
Definite	The Adverse Event is clearly related to the investigational agent(s)

1.19.6 What to do in the event of a serious adverse event

The investigator must report any Expected Serious Adverse Event (SAE-E) or Unexpected Serious Adverse Event (SAE-U) and adverse events of special interest (AESI) (see section 19.7) that occurs during the treatment period starting at the time consent is signed, or within 30 days after the last administration of the study drug, regardless of whether it is attributable to the study. The event must be reported within 24 hours of learning of the event to the Yale Project Manager and Sponsor PI who will report to Boehringer Ingelheim. Sites are responsible for reporting to their IRB per local policy. All events will be forwarded by the PM to Boehringer Ingelheim as required.

All SAEs should be entered into OnCore within 24 hours of the site becoming aware of the event.

The Yale Project Manager shall provide SAEs and AESI to BI as per the method and timeline specified in section 1:19.9

Any delayed serious adverse event (occurring after the 30-day period) that may reasonably be considered related to the treatment(s) described in the protocol or to the study must be reported, and no time limit applies to such adverse events.

For each event, the investigator shall complete the SAE reporting form provided at start-up.

Additional information may be requested by the monitor (by fax, post, telephone, or during a visit).

Nevertheless, any event that qualifies as expected but differs in its intensity, clinical course, or frequency will be considered as an unexpected event by the pharmacovigilance unit at Boehringer Ingelheim.

1.19.7 Adverse events and laboratory values of special interest

The following events are considered as Protocol-specified events of special interests:

Any gastrointestinal- and non-gastrointestinal perforation, leakage, fistula formation, abscess

- In such cases the following additional information needs to be collected, documented in the respective comment field of the CRF page and the respective narratives of the SAE form and emailed or faxed to the Yale Project Manager and Sponsor PI.
- Location of perforation, leakage, fistula, abscess
- Location/extent of abdominal tumor manifestations,
- Imaging & reports (CT, ultrasound, endoscopy, pathology, etc.)
- Prior surgery (location, wound healing complications)
- Concomitant diseases with GI involvement (e.g., M Crohn, vasculitis, tuberculosis, diverticulitis)
- Thromboembolic events (or predisposition)

Drug-induced liver injury is under constant surveillance by sponsors and regulators and is considered a protocol-specified adverse event of special interest (AESI). Timely detection, evaluation, and follow-up of laboratory alterations of selected liver laboratory parameters to distinguish an effect of the investigational drug from other causes are important for patient safety and for the medical and scientific interpretation of the finding.

The following are considered as protocol-specified AESI:

- An elevation of ALT and / or AST >5x ULN without bilirubin elevation measured in the same blood draw sample
- An elevation of AST and/or ALT >2.5 fold ULN combined with an elevation of bilirubin to >1.5 fold ULN measured in the same blood draw sample

Patients showing above laboratory abnormalities need to be followed up until the protocol specific retreatment criteria have been met.

Protocol-specified AESI are to be reported in an expedited manner to the PM to BI, similar to Serious Adverse Events, even if they do not meet any of the seriousness criteria.

1.19.8 Reporting to the IRB

Sites are responsible for reporting to their IRB per local policy.

The PM will report to the Yale IRB all SAEs meeting the criteria for expedited reporting using HIC Form 710 FR 4: Unanticipated Problem Involving Risks to Subjects or Others (UPIRSOs), including Adverse Events (AEs) Reporting Form as per Yale IRB Policy 710.

1.19.9 Reporting to Boehringer Ingelheim

Upon inclusion into a trial, the patient's condition is assessed (e.g. documentation of history / concomitant diagnoses and diseases), and relevant changes from baseline are noted subsequently.

All adverse events, serious and non-serious, that occur from the time of signing the informed consent through 30 days following cessation of Nintedanib will be collected and documented by the investigator.

The Yale Project Manager shall report all SAEs and non-serious AEs which are relevant to a reported SAE by fax using BI's SAE form to BI Unique Entry Point as detailed below in accordance with the following timelines:

- within five (5) calendar days upon receipt of initial and follow-up SAEs containing at least one fatal or immediately life-threatening event;
- within ten (10) calendar days upon receipt of any other initial and follow-up SAEs.

Boehringer Ingelheim Pharmaceuticals, Inc.

[name]

[name]

[contact]

For each adverse event, the investigator will provide the onset date, end date, intensity, treatment required, outcome, seriousness, causal relationship and action taken with the investigational drug.

The investigator will also determine the expectedness of each AE based on the listed adverse event section of Boehringer Ingelheim's (BI's) Investigator Brochure for the Product.

The investigator does not need to actively monitor patients for adverse events once the clinical trial has ended. However, if the investigator becomes aware of an SAE(s) that occurred after the patient has completed the clinical trial (including any protocol specified follow-up period/Residual effect period), it should be reported to the PM if investigator considers it as relevant to the study drug. The PM will report to BI as required.

1.19.10 *Follow-up of SAEs*

The investigator is responsible for providing appropriate medical follow-up for patients until the event has resolved or stabilized or until the patient's death. Sometimes this may mean that follow-up will extend beyond the patient's withdrawal from the trial.

The investigator shall send additional information to the Project Manager and Sponsor PI using the SAE report form provided at start-up specifying that this is a follow-up report and not an initial report) within 48 hours of receiving the information. The investigator must also send the final follow-up once the SAE has resolved or stabilized.

The investigator shall keep the documents about the presumed adverse effect, in case anything needs to be added to the information previously sent.

The investigator shall respond to requests for additional information in order to document the initial report.

If an SAE is suspected of having been caused by Nintedanib, the Project Manager shall send the report to BI.

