1.10.1 Screening period

The screening period is the time preceding registration and includes the 14-day period for performing screening assessments.

The following assessments will be completed within 2 weeks prior to the first dose of study drug:

- Informed Consent
- Medical history,
- Complete physical examination,
- Body weight, height and vital signs,
- ECOG performance status,
- EKG,
- Chest X-ray,
- assess left ventricular ejection fraction (LVEF); using 3D Echocardiogram or the biplane Simpson method.
- Concomitant medication,
- Hematology: Complete Blood Cell Count (CBC) with differential (differential done as per hospital standard of care) entire panel is required at screening
- Serum chemistry: AST, ALT, alkaline phosphatase, total bilirubin, BUN, serum creatinine, glucose, calcium, sodium, potassium, magnesium, chloride, bicarbonate, total protein, albumin, uric acid, LDH, and Beta HCG (women of childbearing potential only)

- Hepatitis B and C, HIV1 and 2 serologies
- Coagulation profile: prothrombin time, activated partial-thromboplastin time, fibrinogen,
- Additional examination when clinically indicated (lumbar puncture, CT-scan, PET CT scan).
- Bone marrow evaluation including a new cytogenetic and molecular characterization at the time of relapse,
- Pharmacodynamic assessment: collection of blood (5 x 4mL) and bone marrow samples (8mL).

The following assessments will be performed just prior to treatment from day – 1 to 1: If these tests are performed within 24 hours of the Cycle 1 Day 1 visit, prior to administration of study drug, they do not need to be repeated on Cycle 1 Day 1, unless otherwise determined by the Principal Investigator.

- Physical examination,
- Body weight,
- ECOG performance status,
- Hematology = CBC with differential (differential done per hospital standard of care)
- Serum chemistry. It includes AST, ALT, alkaline phosphatase, total bilirubin, BUN, serum creatinine, glucose, calcium, sodium, potassium, magnesium, chloride, bicarbonate, total protein, albumin and LDH.
- Coagulation profile: prothrombin time, activated partial-thromboplastin time, fibrinogen,
- Bacterial, fungal and viral cultures of throat, stool and urine, if clinically indicated,
- Pregnancy test (women of childbearing potential only)

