1.10.2 Evaluation during treatment period

The treatment period begins Cycle 1 Day 1 and can continue until up to 30 days after the last dose of Nintedanib. The treatment period can include a maximum of 2 (28 day) induction and 2 (28 day) consolidation cycles. If Maintenance therapy is indicated, patients will be followed monthly for the first 12 months and then every three months for the following year (a maximum of 24 months). Number and type of cycle will vary by patient and according to local SOC procedures.

Labs between day 8 and counts recovery can be done +/-2day

The following assessments need to be completed:

- Physical examination daily from day 1 to day 6 and then twice weekly during the induction cycle(s) 1 and 2 (if receiving a second cycle). During consolidation cycle(s) 1 and 2 at day 1, then weekly, and at the end of each cycle.
- ECOG performance status weekly during the first induction cycle and at the end of each cycle thereafter,
- Any adverse event,
- Concomitant medication,
- CBC with differential daily from day 1 to day 5 and then every other day for the first cycle and three times weekly of each cycle thereafter, (differential done as per hospital standard of care) entire panel required at response evaluation
- Serum chemistry daily from day 1-5. Then at a minimum of twice weekly, 3-4 days apart (+/- 2 days) during the first cycle and every other week each cycle thereafter. It includes AST, ALT, alkaline phosphatase, total bilirubin, BUN, serum creatinine, glucose, calcium, sodium, potassium, chloride, bicarbonate, total protein, albumin, LDH and magnesium
- Pregnancy test prior the beginning of each new treatment cycle (women of childbearing potential only)
- Coagulation profile daily from Day 1-5 of cycle 1 and then weekly during the first two cycles: prothrombin time, activated partial-thromboplastin time, fibrinogen,
- Bone marrow evaluation will be performed in patients with complete clearance of blasts in the blood on Day 14 (+/- 1 day) and at the end of cycle 1 Day 28 (+/- 7 days) and decided by local investigator based on count recovery. Threshold: ANC at 1 and PLT at 50,
- Assess LVEF before cycle 2; this can be done any time after Cycle 1 day 14 up to the start of cycle 2, ideally closer to cycle 2 Day 1 using 3D Echocardiogram or the biplane Simpson method.

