1.10.4 End of study treatment evaluation

A clinical work-up is to be performed at the end of treatment with Nintedanib within 30 days after the last administration of Nintedanib:

- Complete physical examination,
- Weight,
- ECOG performance status,
- Vital signs,
- Any adverse event,
- EKG,
- Assess LVEF, using 3D Echocardiogram or the biplane Simpson method, after Cycle 1 EOT visit ONLY
- Concomitant medication,
- Hematology: CBC with differential and hemoglobin,

- Serum chemistry including AST, ALT, alkaline phosphatase, total bilirubin, BUN, serum creatinine, glucose, calcium, sodium, potassium, magnesium, chloride, bicarbonate, total protein, albumin, and LDH
- Bone marrow evaluation will be performed in patients with complete clearance of blasts in the blood,
- Pregnancy test up to 3 months after last dose of Nintedanib (women of childbearing potential only)
- Pharmacodynamic assessment: collection of blood (5 x 4mL) and bone marrow samples (5-6 mL if a bone marrow aspirate is performed).

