1.25.7 Study Calendar

Screening and Cycle 1 (Induction Therapy)

	Screening		Day																								END Of Treatment		
	-14 to - 5	-1	1	2	3	4	5	6	7	8	9	10	11	12	13	14	15	16	17	18	19	20	21	22	23	24	25	26	27
Informed Consent	x																												
Medical History	x																												
Additional exams (Lumbar puncture, CT, Pet-CT) ^b	x																												
EKG, Cardiac Echo, and CXR ^m	x																												x
Hepatitis B, C, HIV1 & HIV2 serologies	x																												
Bacterial, fungal & viral cultures throat, stool & urine ^b		x																											
Bone Marrow Evaluation & Cytogenetics	x																												
Correlative Studies (Blood)	x									x ^l							x ^l										x	x	
Correlative Studies (Bone Marrow)	x								x ^{gl}							x ^l											x	x	
Concomitant Medications ^q	x																												
Bone Marrow Biopsy ^k																x ^l												x ^p	x
Physical Exam ^{c, 0}	x	x	x ^a	x	x	x	x	x		x ^h		x ^h		x	x														
ECOG PS	x	x				x ⁱ					x ⁱ				x ⁱ			x ⁱ			x ⁱ							x	
CBC with differential ⁿ	x	x	x ^a	x	x	x	x	x	x ^j	x ^j	x ^j	x ^j	x ^j	x ^j	x ^j	x ^j	x ^j	x ^j	x ^j	x ^j	x ^j	x ^j	x ⁱ	x ⁱ	x ⁱ	x ⁱ	x		
Serum chemistry ^d	x	x	x ^a	x	x	x	x	x		x ^h	x ^h		x ^h			x ^h		x											
Pregnancy testing	x	x	x ^a																										
Coagulation Profile ^e	x	x	x ^a	x	x	x	x	x		x ⁱ				x ⁱ					x ⁱ										
Idarubicin ^f			x	x	x																								
Cytarabine			x	x	x																								
Study Drug (nintedanib/placebo)									x ^g	x	x	x	x	x	x	x	x	x	x	x	x	x	x	x	x	x	x		
AEs ^q																													

a: If these tests are performed within 24 hours of the Cycle 1 Day 1 visit, prior to administration of study drug, they do not need to be repeated on C1 D1, unless otherwise determined by the Principal Investigator.

b: If clinically indicated

c: Complete physical exam and vitals including, weight, blood pressure, pulse, temperature, respiratory frequency, height required at screening only

d: Serum chemistry: AST, ALT, alkaline phosphatase, total bilirubin, BUN, serum creatinine, glucose, calcium, sodium, potassium, magnesium, chloride, bicarbonate, total protein, albumin, LDH, **and uric acid at screening only**

e: Coagulation profile: prothrombin time, activated partial-thromboplastin time, and fibrinogen,

f: Idarubicin may be dose reduced, replace, or omitted according to total dose of anthracycline received by the patient

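### The end of AE collection and the end-of-treatment work-up are timed from nintedanib alone, which can shorten non-serious AE follow-up when a later cycle's chemotherapy is given and nintedanib is not taken

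*Combined protocol and SAP*

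**What the plan says.** Three provisions use nintedanib as the only clock:

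- Section 1.19.9: all AEs, serious or not, "that occur from the time of signing the informed consent through 30 days following cessation of Nintedanib will be collected".
- Section 1.10.2: the treatment period "can continue until up to 30 days after the last dose of Nintedanib".
- Section 1.10.4: the closing clinical work-up, which includes an AE check, is done "at the end of treatment with Nintedanib within 30 days after the last administration of Nintedanib".

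SAEs and AEs of special interest have their own rule in section 1.19.6. They are reportable if the event "occurs during the treatment period starting at the time consent is signed, or within 30 days after the last administration of the study drug". A later SAE "that may reasonably be considered related to the treatment(s) described in the protocol or to the study must be reported", with no time limit.

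Other text bears on the end of collection without fixing it. Section 1.19.1 requires AEs to be reported from consent onward and gives no end date. Section 1.10.2 lists AEs among the treatment-period assessments and adds: "The treatment period can include a maximum of 2 (28 day) induction and 2 (28 day) consolidation cycles". Section 1.20.2 asks for toxicity data at the end of every cycle, and footnote o of the cycle 2-4 calendar (1.25.7) calls for ongoing AE assessment. The long-term follow-up in section 1.18 collects subsequent therapy, progression or relapse, and death, but not AEs.

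**The concern.** Within a cycle the two treatments are separated in time: chemotherapy on days 1-3, no drug on days 4-7, nintedanib or placebo from day 8. A patient can therefore receive a later cycle's chemotherapy and no further nintedanib. The plainest case is a patient who starts that cycle and stops before day 8, for example for toxicity or progression, which section 1.15 allows. A second is nintedanib permanently stopped for a liver signal (Table 4 in 1.5.2.3) with chemotherapy continued. The protocol neither authorises nor forbids this.

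For such patients the 30-day clock may have started in the previous cycle. The safety analysis in 1.20.2 counts all AEs in everyone with at least one dose of therapy, and comparative safety is a Phase II secondary objective (1.3.2). The end date for non-serious AEs would then depend on when one component stopped, not on when treatment stopped, and two sites could apply different end dates to the same situation.

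**Working it through.** The plan gives no figure to reproduce; this is a day count.

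**Inputs from the protocol.** Chemotherapy on cycle days 1-3 and nintedanib on days 8-28 (1.1, 1.25.7); 28-day cycles; a 30-day window (1.10.2, 1.10.4, 1.19.9); induction cycle 2 possible from study day 29 (1.5.1).

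**Assumptions.** Nintedanib includes its matching placebo. The last nintedanib dose before the later cycle is on study day L = 28. The later cycle starts on study day S = 29, 35, 45 or 60. Only day 29 is named in the protocol; the others reflect permitted breaks and the wait for count recovery before consolidation. The benchmark is the plan's own 30 days, applied to chemotherapy.

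**Definitions.** Window end W = L + 30 = 58. Last chemotherapy day = S + 2. Thirty days after it = S + 32. Last day of the cycle = S + 27. Cycle day 7 = S + 6.

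**Step 1: a cycle with at least one nintedanib dose.** The earliest such dose is on S + 7, so the window ends no earlier than S + 7 + 30 = S + 37, after S + 32. There is no gap. In cycle 1 this is day 38 against day 33. A full cycle 1 is covered to day 58, 55 days after chemotherapy ended on day 3.

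**Step 2: a later cycle without nintedanib, AEs recorded through each cycle.** Uncovered days are:

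- cycle completed: (S + 32) − max(W, S + 27);
- patient leaves on cycle day 7, cessation read as the last capsule: (S + 32) − max(W, S + 6).

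| S | S + 32 | Cycle completed | Leaves on cycle day 7 |
|---|---|---|---|
| 29 | 61 | 61 − 58 = 3 | 61 − 58 = 3 |
| 35 | 67 | 67 − 62 = 5 | 67 − 58 = 9 |
| 45 | 77 | 77 − 72 = 5 | 77 − 58 = 19 |
| 60 | 92 | 92 − 87 = 5 | 92 − 66 = 26 |

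The maxima are 32 − 27 = 5 and 32 − 6 = 26 whatever S is. If nintedanib had ended early, say on day 14 (W = 44), the columns become 5, 5, 5, 5 and 17, 23, 26, 26.

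**Step 3: cessation read as the date of the decision to stop.** A decision on cycle day 7 gives a window end of S + 6 + 30 = S + 36, after S + 32. Under 1.19.9 the early leaver then has no gap. Sections 1.10.2 and 1.10.4 refer to the last dose or administration, so this reading does not help there. Nor does it help when the decision to stop nintedanib was made in an earlier cycle.

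**Step 4: SAEs.** A related SAE is reportable at any time. An unrelated one is lost only if *study drug* in 1.19.6 means nintedanib/placebo and the event also falls outside the treatment period. The term is not used consistently. The calendar row reads "Study Drug (nintedanib/placebo", whereas 1.10.1 says "If these tests are performed within 24 hours of the Cycle 1 Day 1 visit, prior to administration of study drug" of a day on which only chemotherapy is given.

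**The case against.** The strongest reply is that the triggering situation is not planned. Section 1.5.1 writes later cycles as combination treatment, and in Phase II a patient who cannot tolerate 100 mg is taken off treatment (1.5.2.3). This stands as a limit on frequency. It does not remove the patient who starts a combination cycle and stops before day 8, which needs no departure from protocol.

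Second, 1.19.9 speaks of cessation, and a patient on drug-free cycle day 5 who is still due nintedanib has arguably not ceased it. This stands too: on that reading the early leaver has no gap under 1.19.9. But the protocol does not define the term.

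Third, 1.19.1 sets no end date, and 1.10.2, 1.20.2 and footnote o cover days within a cycle. They reduce the gap and are credited above. None sets an end date after chemotherapy or says that it overrides 1.19.9. Section 1.15 promises early stoppers the same follow-up where possible, but that follow-up carries the same nintedanib clock.

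Fourth, no document requires 30 days after chemotherapy. That is correct; the benchmark is this review's extension of the plan's own window.

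A reader might infer three stronger things:

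- **Loss of the whole 30 days.** Applying the 30-day rule literally gives min(30, S + 32 − W) = 3, 9, 19 and 30 days. This requires sites to stop recording AEs while giving inpatient chemotherapy, contrary to 1.10.2, 1.20.2 and footnote o.
- **A work-up due before chemotherapy ends.** W minus the last chemotherapy day is 58 − 31 = 27, 58 − 37 = 21, 58 − 47 = 11 and 58 − 62 = −4. The negative value rests on an assumed day-60 start, and the cycle 2-4 calendar places End of Treatment after day 28 of the cycle.
- **A general loss of SAEs.** The unlimited rule for related SAEs and the two conditions in Step 4 rule this out.

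**Conclusion.** The point holds in a narrow form, and it is minor. The wording ties the end of AE collection, of the treatment period and of the work-up to one component of a multi-drug regimen. The consequence is confined to later cycles in which chemotherapy is given and nintedanib is not taken. There, 3 to 5 days are uncovered if the cycle is completed. If the patient leaves before day 8, the gap is up to 26 days or, under 1.19.9, none, depending on what cessation means. These figures assume that in-cycle AE recording is done, and those for the early leaver also rest on assumed start days.

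The number of patients is unknown and probably small. The exposure is mainly non-serious AEs. A patient who never starts nintedanib has no cut-off imposed, only no stated end date. The Phase I primary objective concerns safety after one cycle (1.3.1), where this gap cannot arise, and the Phase II primary endpoint is remission after one cycle. No DLT rule or stopping rule changes.

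**What to change.** In sections 1.10.2, 1.10.4, 1.19.6 and 1.19.9, run the 30-day window and the work-up from the last dose of any protocol treatment, whichever is latest: idarubicin or its etoposide replacement, cytarabine, or nintedanib/placebo. For a cycle 2 started on day 29 without nintedanib, coverage would then reach day 31 + 30 = 61. Cycles with nintedanib completed would not change. The same wording settles what *study drug* means in 1.19.6 and gives an end date for patients who never start nintedanib.

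The cost is a wording change in four sections and a few more days to weeks of AE recording for a few patients.
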